**Table 1. Schedule of Activities**

Protocol Activity	Screen  -28 days from enrollment	Cycles 1-6			End of Treatment (EOT)  (All patients: 4 weeks from the last dose of study drug)
		Day 1	Day 8	Day 15	

6. Hepatitis B (HbsAg) and C (anti-HCV) tests. A recombinant immunoblot assay (RIBA) or nucleic acid test (NAT) may be done to confirm or rule out HCV infection as clinically indicated.
7. Urinalysis: conducted at screening, within 72 hours prior to dosing of Cycle 4 Day 1, and the end-of-treatment visit. Urine protein to creatinine ratio will be calculated at screening and End of treatment only.
8. Coagulation: PT/INR collected at screening, up to 72 hours predose of Day 1 of each cycle and EOT. PTT or APTT required at screening and end-of-treatment visits only
9. For women of childbearing potential, beta-human chorionic gonadotropin ( $\beta$ -HCG) serum or urine pregnancy test will be performed at screening, up to 72 hours prior to dosing at Day 1 each cycle, and EOT. Additional pregnancy tests may be done as required by local regulations and/or EC/IRBs.
10. ECGs will be done in triplicate (3 consecutive ECGs approximately 2 minutes apart) in all patients at screening, during treatment Cycles 1, 2 and 4, and EOT. Screening ECG will be done approximately 3-28 days prior to enrollment.
11. LVEF will be assessed at screening either by echocardiogram (ECHO) or Multigated Acquisition Scan (MUGA). Additional assessments may be done during the study if clinically required.
12. Patients must be treated within 3 days from enrollment. If extenuating circumstances prevent a patient from beginning treatment within this time, the patient may begin treatment only with written permission by the Pfizer Clinician.
13. Bone marrow aspirate and disease assessments will be performed at screening, at Day 16-28 of Cycles 1, 2, or until CR/CRi and MRD negativity are achieved. Then after every 1- 2 cycle as clinically indicated, and at EOT visit (unless previously done within 28 days). Bone marrow aspirates will be analyzed at the study site. A CBC with platelets and differential must accompany each bone marrow assessment. Disease assessments will include clinical evaluation of liver and spleen, and other sites of prior or suspected extramedullary disease. Disease assessments will continue until progression. For those who have not progressed at EOT, disease will be assessed every 12 weeks ( $\pm$ 1 week) up to 1 year from enrollment and every 24 weeks ( $\pm$ 2 weeks) between year 1 and 2, and whenever clinically indicated, until progression. All disease assessment results will be captured in the CRF, even if unplanned or not required by protocol.
14. Minimal residual disease (MRD): Bone marrow aspirate will be collected at screening, investigator suspected CR/CRi, achievement of CR/CRi until MRD negativity before EOT. MRD will be assessed using NGS for rearranged IgH, IgK, and IgL receptor gene sequences at a central laboratory.

Immunophenotyping: performed on peripheral blood or bone marrow aspirate with flow cytometry at screening and will be done in patients with suspected CR and/or CRi. IHC is allowed in patients with a dry tap or otherwise inadequate bone marrow aspirate in the absence of circulating blasts. The leukemia phenotype and/or genotype may also be evaluated by other test methods at the discretion of the investigator.

FISH: Bone marrow aspirates may be analyzed by fluorescence in situ hybridization analysis (FISH) for detection of chromosomal aberrations at screening according to standard of care.

Karyotyping: in all patients, at screening and at least once in patients achieving CR or CRi who had abnormal cytogenetics at baseline. It is recommended that 20 or more metaphases be counted for cytogenetics analysis.

Bone Marrow Biopsy: required at least once, to assess cellularity, in patients with CRi by investigator assessment (ANC  $<1 \times 10^9/L$  and/or platelets  $<100 \times 10^9/L$ ) and as clinically indicated per local standard of care. Biopsies may be also required for inadequate aspirate samples

**Table 1. Schedule of Activities**

Protocol Activity	Screen  -28 days from enrollment	Cycles 1-6			End of Treatment (EOT) (All patients: 4 weeks from the last dose of study drug)
		Day 1	Day 8	Day 15	

15. Radiological assessments (ie, computed tomography scan or MRI) will be done at screening for patients with suspected extramedullary disease, during study as clinically indicated and to confirm CR or CRi in patients with extramedullary disease at screening. Please use the same method of assessment for each evaluation. Computed tomography scan with contrast is the preferred method of assessment.
16. AEs will be followed until the event or its sequelae resolve or stabilize at a level acceptable to the investigator, or longer if requested by the sponsor. The AE reporting period continues until 9 weeks after the last dose of investigational drug. However, VOD/SOS events, irrespective of the grade, causality, will be reported in the CRF for up to 2 years from first dose and will also be reported as SAEs.
17. Assessment(s) and test(s) done according to standard of care at the institution prior to the patient signing the ICD can be used to determine patient eligibility if collected within the timeframe specified in this protocol, e.g. procedures conducted within 28 days (ECG 3-28 days) prior to enrollment. Results will be recorded in the CRF. However before any collected sample (e.g. ECG, BM aspirate for disease assessment) is sent to the central vendor, the patient must be consented for study participation.
18. Assessment of CNS disease (eg, lumbar puncture) is required at screening in any patient with a prior history of CNS disease or if CNS disease is suspected due to clinical signs and/or symptoms. If a complete CNS assessment is not feasible due to comorbidities, the patient cannot be included in the study. If additional assessments are done at the site, as clinically indicated, results must be collected in the CRF. Patients with history of CNS disease who achieve a CR or CRi must have a CNS assessment to confirm complete response.
19. EOT visits should be performed before starting a new anti-leukemic therapy (including before subsequent hematopoietic stem cell transplant (HSCT) conditioning, other form of consolidation/intensification or maintenance therapy). If a new anti-leukemia therapy will be started, the EOT visit should occur as close as possible to 4 weeks after the last dose of study drug.

**Table 2. Long Term Follow-Up**

Study Procedures	Disease Follow-up 	Survival Follow-up 
Study Visit	Every 12-24 weeks 	Every 12 weeks
Serum chemistry 	X	
Hematology 	X	
Coagulation test (INR/PT) 	X	
ECOG performance status	X	
Bone marrow aspirate and disease assessments 	X	
Other anticancer therapy 	X	X
Survival status 	X	X

1. Disease follow-up: For patients who have discontinued treatment but have not progressed, (including patients undergoing stem-cell transplant or other subsequent anti-leukemic therapy), starting approximately 12 weeks after the last disease assessment, until disease progression for up to 2 years after Day 1 Cycle 1, disease will be assessed every 12 weeks ( $\pm 1$  week) up to 1 year from Cycle 1 Day 1 and every 24 weeks ( $\pm 2$  weeks) between year 1 and 2, and whenever clinically indicated, until relapse.
2. Survival follow-up: All patients (including patients undergoing stem-cell transplant or other subsequent anti-leukemic therapy) starting approximately 12 weeks ( $\pm 1$  week) after documented disease progression and continuing approximately every 12 weeks ( $\pm 1$  week) for up to 2 years after Day 1 cycle 1 for each patient. It can be conducted by telephone or email.
3. Coagulation, hematology and serum chemistry (limited to total bilirubin, alkaline phosphatase, ALT, AST, GGT, LDH and albumin) required for one year after Cycle 1 Day 1 or until new anti-cancer treatment, whichever occurs first. For patients in disease follow up beyond a year from Cycle 1 Day 1, CBC with differential and platelets required until disease progression.
4. Bone marrow aspirate and extramedullary disease assessments. Performed every 12 weeks ( $\pm 1$  week) for 1 year from Cycle 1 Day 1, and every 24 weeks ( $\pm 2$  weeks) between year 1 and 2, and whenever clinically indicated. Disease assessments include liver and spleen assessments. No bone marrow aspirate is necessary if non-response or progressive disease/relapse can be diagnosed from peripheral blood evaluation.
5. To include anticancer medications, cancer-related radiotherapy, and cancer-related surgical therapies. Start/stop date will be collected for 2 years (total, relative to the day of enrollment). Also at least the first post-study salvage therapy (re-induction) and response to the first post study salvage therapy (re-induction) will be reported in the CRF (refractory or responsive disease). Post-study transplant information including conditioning treatments will be collected for up to 2 years from enrollment. Select concomitant medications including antifungals, prophylaxis/treatment for graft vs host disease, and prophylaxis/treatment for VOD will be collected for up to at least 100 days after HSCT.

PK samples will be collected for all patients and ECG in triplicate will be done for all patients.

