Patients who achieve a response to treatment and who have a suitable donor may undergo stem-cell transplantation at the discretion of the investigator. No association between the time from last dose of inotuzumab ozogamicin to HSCT and outcomes after HSCT has been observed. The potential risk of relapse after the last dose of inotuzumab ozogamicin must be balanced against the potential risk of toxicity associated with beginning HSCT soon after the last dose of inotuzumab ozogamicin.

All cases of VOD/sinusoidal obstruction syndrome (SOS) irrespective of causality or severity will be reported as serious adverse events (SAEs) for up to 2 years after the first dose of inotuzumab ozogamicin. An independent hepatic event adjudication committee will evaluate safety for potential VOD/SOS events and Hy's law cases. Survival will be followed up to 2 years from first dose.

PK samples will be collected for all 44 patients in the study to describe population PK profiles.

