#### 4.4. End of Study Definition

A participant is considered to have completed the study if he/she has completed all phases of the study including screening, treatment period, disease follow up and survival follow up. For each patient survival follow up will start after documented disease progression and continuing for up to 2 years from the first dose (Day 1 Cycle 1).

The end of the study is defined as the date of the last participant completion of survival follow up, it will be up to 2 years from first dose of the last patient. Survival follow up can be conducted by telephone or email.

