### **7. DISCONTINUATION OF STUDY INTERVENTION AND PARTICIPANT DISCONTINUATION/WITHDRAWAL**

#### **7.1. Discontinuation of Study Intervention**

Per the study estimands, if investigational product is permanently discontinued, the participant will remain in the study and continue to be followed for protocol specified follow up procedures. The only exception to this is when a patient specifically withdraws consent for any further contact with him or her or persons previously authorized by the patient to provide this information.

It may be necessary for a participant to permanently discontinue study intervention. Reasons for permanent discontinuation of study intervention include the following:

- Objective disease progression;
- Lack of efficacy
- Global deterioration of health status requiring discontinuation;
- Unacceptable toxicity;
- Pregnancy;
- Significant protocol violation;
- Lost to follow-up;
- Participant refused further treatment;
- Study terminated by sponsor;
- Death.

Note that discontinuation of study intervention does not represent withdrawal from the study. If study intervention is permanently discontinued, the participant should remain in the study to be evaluated for safety, disease assessments, subsequent anticancer therapies, and survival. See the [SoA](#) for data to be collected at the time of discontinuation of study intervention and follow-up and for any further evaluations that need to be completed.

In the event of discontinuation of study intervention, it must be documented on the appropriate CRF/in the medical records whether the participant is discontinuing further receipt of study intervention or also from study procedures, posttreatment study follow-up, and/or future collection of additional information.

Following the discontinuation from the treatment, patients will be followed for:

1. Disease progression for up to 2 years from the first dose, unless the disease progressed during the treatment.
2. Potential VOD/SOS cases, irrespective of grade or causality for up to 2 years from the first dose.
3. Survival for up to 2 years from the first dose.

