6.2. Secondary Endpoint(s)

6.2.1. Overall Survival

Estimand strategy: treatment policy.

Analysis set: Safety analysis set.

Analysis methodology: using Kaplan-Meier method, plot the estimation of the survival function and estimate its associated statistics on OS (including the quartiles of OS with two-sided 95% CI, the OS rates at clinical meaningful timepoints with two-sided 95% CI). The CI for the quartiles will be calculated according to Brookmeyer and Crowley method, and the CIs for the survival probability estimates at the timepoints will be derived using the log(-log) method.

Intercurrent events: the analysis is conducted without regard to discontinuation from treatment or start of new anti-cancer therapy.

Participants without confirmation of death will be censored on date of last contact.

Frequency (number and percentage) of participants with an event (death) and censoring reasons will be presented. Censoring reasons are as follows: alive, withdrawal of consent and lost to follow-up.

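### Survival contact starts only after progression, so non-progressed patients have only 24-weekly routine survival status in year 2, and no patient has a fixed contact at 24 months

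*Protocol*

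**What the plan says.** **The commitment.** The synopsis (Protocol 1.1, Overall Design) says "Survival will be followed up to 2 years from first dose". Section 7.1, and the matching list in Section 1.1, set out what patients are followed for after stopping treatment. Survival is its own item, separate from disease progression and with no progression condition: "Survival for up to 2 years from the first dose".

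**Disease follow-up (Table 2, footnote 1).** This covers patients who have stopped treatment without progressing. It begins "starting approximately 12 weeks after the last disease assessment" and continues "until disease progression for up to 2 years after Day 1 Cycle 1, disease will be assessed every 12 weeks" (±1 week) to 1 year, then every 24 weeks (±2 weeks) in year 2, with extra visits when clinically indicated. The survival status row is ticked for these visits.

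**Survival follow-up (Table 2, footnote 2).** The footnote opens by addressing all patients, but the contact is defined as starting about 12 weeks "after documented disease progression and continuing approximately every 12 weeks", "for up to 2 years after Day 1 cycle 1 for each patient. It can be conducted by telephone or email". Section 4.4 repeats the trigger: "For each patient survival follow up will start after documented disease progression and continuing for up to 2 years from the first dose".

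**Closing contact.** Table 2 schedules none, at 2 years or at end of study.

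**Analysis.** SAP 6.2.1 states "Participants without confirmation of death will be censored on date of last contact". SAP 5.2.6 takes the date of last contact as the latest of several sources: assessments, concomitant and subsequent therapy dates, adverse event dates, the Survival Follow-up CRF, and the disposition page unless the reason is loss to follow-up or death. SAP 6.2.1 also asks for OS rates at clinically relevant times without naming them.

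**The concern.** Read literally, a patient who never progresses never enters the survival phase. That patient's survival status comes only from disease visits, which are 24 weeks apart in year 2 and do not land on 24 months. These patients, many of them probably transplanted, shape the late part of the OS curve.

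Two things are at stake:

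- **Precision.** A 24-month OS estimate needs patients known to be alive at 24 months, and the routine schedule does not ensure that.
- **Unequal ascertainment by progression status.** A death reported between visits is counted on its date, while a living patient is censored at the last contact. If deaths reach the site faster than confirmation that a patient is alive, the late Kaplan-Meier curve is pulled down. The longer interval makes this more likely in the non-progressed group.

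**Working it through.** **1. The stated horizon.** SAP 5.2.11 sets 1 year = 365.25 days. One year is 365.25/7 = 52.2 weeks, and 2 years is 2 × 365.25/7 = 104.4 weeks.

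**2. Non-progressed patients, nominal visits (Table 2, footnote 1).** The last 12-weekly visit is the last one on or before week 52.2, so it lies between weeks 52.2 − 12 = 40.2 and 52.2.

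- First year-2 visit (+24): weeks 64.2 to 76.2.
- Second year-2 visit (+24): weeks 88.2 to 100.2.
- A third (+24) would fall at weeks 112.2 to 124.2, beyond 104.4.

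The last nominal visit is therefore at about weeks 88 to 100. The shortfall runs from 104.4 − 100.2 = 4.2 to 104.4 − 88.2 = 16.2 weeks. Stepping the calendar from a last on-treatment or end-of-treatment assessment at weeks 3 to 32 (an assumed range, in quarter-week steps) gives 88.25 to 100.0, a shortfall of 4.4 to 16.1 weeks.

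Two specific readings:

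- Anchored to Cycle 1 Day 1, the visits are weeks 12, 24, 36, 48, 72 and 96: 104.4 − 96 = 8.4 weeks short.
- With year-2 visits counted from week 52, they are weeks 76 and 100: 4.4 weeks short.

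**3. Visit windows.** On a fixed grid with ±2 weeks, the last visit lies at about weeks 86 to 102. If each interval drifts within its own window, the range is about 84 to 104 with a median near 94. With windows simulated as uniform, about 0.6% of last visits fall within 2 weeks of 24 months.

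**4. Progressed survivors (Table 2, footnote 2).** With 12-week steps the last contact lies between 104.4 − 12 = 92.4 and 104.4, that is, at about weeks 92 to 104. No contact is fixed at 24 months here either.

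**5. Age of survival status.** In year 2 the interval can reach 24 + 2 = 26 weeks without progression and 12 + 1 = 13 weeks after it. These maxima apply to a cutoff falling anywhere in year 2. At 24 months exactly, the nominal ages are about 4 to 16 weeks and 0 to 12 weeks.

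**6. Position on the OS curve.** Median OS with inotuzumab ozogamicin in Study B1931022 was 7.7 months (Protocol 4.2), or 7.7 × 30.4375/7 = 33.5 weeks, well before week 88. The primary analysis cutoff is at least 9 months after the last first dose (SAP Section 2), or 9 × 30.4375/7 = 39.1 weeks. Only earlier-enrolled patients can be in year 2 at the earliest permitted cutoff.

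**7. How many patients.** The documents give no 2-year survival rate. If 10% to 25% of 44 were alive at 2 years (an assumption), that is 4.4 to 11 patients, including progressed survivors. As a cross-check with Study B1931022 figures (Protocol 2.2.2.1), 79/164 had a transplant and 35.4% survived after it: 44 × 79/164 × 0.354 = 7.5. No time point is given for the 35.4%, and not all of these patients would be progression-free. The number affected is a handful and cannot be fixed more closely.

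**The case against.** A reader might infer that every non-progressed survivor is censored at weeks 88 to 100 and that the 2-year follow-up is not delivered. The documents do not support either reading.

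- **Last contact is broader than disease visits.** SAP 5.2.6 also credits therapy, adverse event and disposition dates, and SAP 5.2.10 allows unscheduled assessments. Any such date near 2 years moves censoring there.
- **The commitment is a cap.** The text says up to 2 years, and Section 7.1 applies it whatever the progression status. Veno-occlusive disease and subsequent therapy are also collected to 2 years (Section 8.4.1, Table 2 footnote 5), so sites have reason to stay in touch.
- **Progressed patients also lack a fixed 2-year contact.** The groups differ in interval, not in whether a closing contact exists.
- **Bias is not shown.** Ending follow-up on a schedule does not by itself bias Kaplan-Meier. A downward bias needs deaths to become known between visits when living status does not.
- **OS is a descriptive secondary endpoint** (SAP 5.2), and no 24-month landmark is named.

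All five points stand and limit the claim, but they do not close the gap. SAP 5.2.6 accepts only dates tied to actual examination of the participant, so an administrative completion date may not count. Section 4.4 defines completion through survival follow-up, which for a non-progressed patient has no start and hence no defined closing contact. Routine adverse event collection ends 9 weeks after the last dose. Selected post-transplant medications need be collected only to at least 100 days after transplant. The later sources of a contact date are therefore incidental.

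**Conclusion.** The point holds as an internal inconsistency and a gap in the routine schedule. Table 2 footnote 2 and Section 4.4 make the 12-weekly survival contact conditional on progression; Sections 1.1 and 7.1 do not.

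On the nominal calendar, routine survival status ends at about weeks 88 to 100 without progression and weeks 92 to 104 after it, with no closing contact for either group. Two-year survival follow-up is thus not ensured, which is less than saying that it will not happen.

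The consequence is confined to late OS. A 24-month rate would lose precision, and it could be somewhat too low if deaths are learnt between visits more readily than survival. The size of that bias cannot be derived from the documents. Median OS should not move if it is anywhere near the Phase 3 value, and the primary CR/CRi test is untouched.

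The week ranges assume that visits follow the stated intervals; the patient count rests on assumed survival rates. This is a cheap improvement worth making, not a flaw in the primary analysis.

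**What to change.** - Reconcile Table 2 footnote 2 and Section 4.4 with Section 7.1, so that survival follow-up applies to every patient who has stopped treatment, whether or not progression has been documented.
- Add one telephone or email vital-status contact at 24 months after Cycle 1 Day 1 for every living patient, for example week 104 with a window of +4 weeks, recorded on the Survival Follow-up CRF. Week 104 is 728 days against 730.5 for 24 months, so the contact should be made on or after the 24-month date if the patient is to count there. The 2-year limit should be worded to allow the window.
- Optionally, add 12-weekly telephone contact for non-progressed patients in year 2. This evens out the age of survival status between the groups, but alone it would still end at about weeks 92 to 104, so it does not replace the closing contact.

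SAP 5.2.6 already uses the Survival Follow-up CRF, so the censoring rule need not change. The cost is a protocol wording change and a few extra contacts per surviving patient, by a method the protocol already allows, with no added clinic visit or marrow sample.

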**Table 3. Pharmacokinetics and ECG Monitoring Flowchart**

Cycle 1											
Cycle Day	1				4	8			15		
Time (h) relative to the start of inotuzumab ozogamicin administration	0	1	2	4	72	0	1	6	0	1	
PK sample collection a	X b	X c	X	X		X	X b	X c	X	X b	X c
ECGs d	X	X									
Cycle 2											
Cycle Day	1			8							
Time (h) relative to the start of inotuzumab ozogamicin administration	0	1	2		0			2			
PK sample collection a	X b	X c	X		X b			X			
ECGs d	X	X									
Cycle 4											
Cycle Day	1			8							
Time (h) relative to the start of inotuzumab ozogamicin administration	0		1					0			
PK sample collection a	X b		X c					X b			
ECGs d	X		X								

